
Group Modifications

Describe necessary changes that will or have been made to the study instruments for different groups. No modifications will be made.

Method for Assigning Subjects to Groups

Describe how subjects will be randomized to groups.

The proposed study is a randomized controlled non-crossover pilot study in which 27 participants will be allocated in a 1:1 ratio to the MBSI-I intervention arm or an education only control arm for a treatment period of four weeks. Assignment by 1:1 simple randomization will occur via the Randomization module in REDCap. A randomization table will be designed and uploaded to the REDCap system, to reflect 1:1 simple randomization.

Administration of Surveys and/or Process

Describe the approximate time and frequency for administering surveys and/or evaluations. For surveys, questionnaires and evaluations presented to groups and in settings such as high schools, focus group sessions or community treatment centers explain how the process will be administered and who will oversee the process. For instance, discuss the potential issues of having teachers and other school personnel administer instruments to minors who are students especially if the content is sensitive in nature. Describe the procedure for audio and videotaping individual interviews and/or focus groups and the storage of the tapes. For instance, if audio tape recording is to be used in a classroom setting, describe how this will be managed if individuals in the class are not participating in the study. Explain if the research involves the review of records (including public databases or registries) with identifiable private information. If so, describe the type of information gathered from the records and if identifiers will be collected and retained with the data after it is retrieved. Describe the kinds of identifiers to be obtained, (i.e. names, social security numbers) and how long the identifiers will be retained and justification for use.

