
Characteristics of the Study Population

Target population

Older adults with insomnia and mild cognitive impairment

Subjects enrolled by Penn Researchers

40

Subjects enrolled by Collaborating Researchers

0

Accrual

ACCESS TO THE POPULATION We plan to recruit 27 participants from three sources: 1) Division of Geriatric Medicine Division Ralston House clinic: There are currently 2,864 active patients, with 40% having mild cognitive impairment (MCI), yielding a potential 1,145 patients with MCI. We will use EPIC to generate a list of eligible participants coming in for clinic visits each week. Staff will introduce patients to the study team for further screening. This first method of recruitment is on hold due to Covid-19. 2) PennSeek search of MCI and insomnia yielded 870 potential participants. After obtaining permission to contact from their provider and completing a telephone screening call, consent and research visits will be set up via telephone or video-conferencing call. 3) Recruitment will also include contacting participants from a recruitment database (I.e., subject registry), which contains names of over 1000 individuals who participated in or were not eligible for study team members' previous or on-going studies and have indicated a willingness to be contacted for future studies. Participant information will be accessed via REDCap, and participants will be contacted by phone to determine interest and eligibility for this study. **ANALYSIS:** Power calculation was done using PASS v21. We initially planned to power the study on two primary outcomes, sleep latency and health related quality of life and required a sample size of 40. However, given that this is a pilot study, Covid-19 and other time constraints, we decided to power the study on our main primary outcome of sleep latency. Thus, the study is powered to detect time averaged difference of two groups in a repeated measures design for the primary, continuous outcome of sleep latency using the generalized estimating equation (GEE) approach. To estimate the necessary sample size, we assumed equal allocation between the treatment and control groups. The minimum time averaged difference in sleep latency between the two groups we were interested in detecting was set at 4.5 minutes with a standard deviation of 4. We expect an even larger effect size, given the work of Cassidy-Eagle et al.⁴² Assuming a baseline correlation $r = 0.80$ between multiple observations from the same subject over time and anticipating 20% attrition, we require 27 total participants in the study to achieve 80% power.

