
The following documents are currently attached to this item:

There are no documents attached for this item.

Deception

Does your project use deception? Deception could be considered any direct misinformation presented to the subject or omission of key information pertaining to the design or nature of the project.

No

International Research

Are you conducting research outside of the United States?

No

Analysis Plan

Power Analysis for Sample Size described previously under "Accrual". Descriptive statistics will be used to characterize the sample, with measures of central tendency and variation for continuous measures, and frequencies and percentages for dichotomous and categorical variables. Descriptive estimates will be generated for all participants at each of the observed time points, and by intervention group within each time point. Distributional assumptions and outliers will be assessed via graphical approaches. Baseline characteristics between groups will be compared appropriate two sample -test or non-parametric Wilcoxon Rank Sum test for continuous variables and Chi-square test for categorical variables. Primary analysis will be carried out under the intent to treat (ITT) framework. To evaluate the difference between groups in our primary outcome, we will utilize the GEE model with time, group, and group by time as the primary predictors. A simple exchangeable correlation structure will be used to model the correlation between multiple observations from the same subject. Given that GEE is less likely to suffer from model convergence, we changed our initial approach from mixed-model to GEE. GEE analysis does not require complete data over time and all available data from all subjects will be used in estimation. We have assumed 20% missingness in our sample size estimation. For missingness more than 20% we will explore imputing missing values when feasible. Given the real time data transmission and ability to call participants and remind them to complete sleep diary, we do not anticipate a great deal of missing data. We will report end of study effect sizes along with p-values and parameter estimates. We will construct reference cell contrasts to evaluate change relative to baseline

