and consecutive time comparisons will be conducted by profile contrasts. It is reasonable to assume due to our sample size GEE models may fail to converge. In such situations we will obtain difference in score between two time points and conduct two sample t-test or Wilcoxon Rank Sum test for two groups comparisons. We will adjust our type I error rate to adjust for multiple comparison under this scenario.

The following documents are currently attached to this item:

There are no documents attached for this item.

Data confidentiality

Paper-based records will be kept in a secure location and only be accessible to personnel involved in the study.

- x Computer-based files will only be made available to personnel involved in the study through the use of access privileges and passwords.**
- x Prior to access to any study-related information, personnel will be required to sign statements agreeing to protect the security and confidentiality of identifiable information.**
- x Wherever feasible, identifiers will be removed from study-related information.**

A Certificate of Confidentiality will be obtained, because the research could place the subject at risk of criminal or civil liability or cause damage to the subject's financial standing, employability, or liability.

A waiver of documentation of consent is being requested, because the only link between the subject and the study would be the consent document and the primary risk is a breach of confidentiality. (This is not an option for FDA-regulated research.)

- x Precautions are in place to ensure the data is secure by using passwords and encryption, because the research involves web-based surveys.**

Audio and/or video recordings will be transcribed and then destroyed to eliminate audible identification of subjects.

Subject Confidentiality

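### Baseline sleep latency is not a covariate in the primary GEE or its fallback; adding it is a cheap improvement worth about 5–6% of the variance at the plan's r = 0.80, and more if the true correlation is lower

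*Combined protocol and SAP*

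**What the plan says.** The Analysis Plan section specifies "the GEE model with time, group, and group by time as the primary predictors", with an exchangeable working correlation. Baseline is one of the three repeated measurements, and the results are read through contrasts: "We will construct reference cell contrasts to evaluate change relative to baseline". If the GEE does not converge, "we will obtain difference in score between two time points and conduct two sample t-test or Wilcoxon Rank Sum test for two groups comparisons".

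No section names baseline sleep latency as a covariate or constrains the arms to a common baseline mean. Calling the listed terms primary predictors does not strictly exclude other covariates, but none is given.

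Two other sections bear on the point. Under Accrual, "the study is powered to detect time averaged difference of two groups in a repeated measures design", with a difference of 4.5 minutes, SD 4, within-subject correlation 0.80 and 20% attrition. Under Method for Assigning Subjects to Groups, "Assignment by 1:1 simple randomization will occur via the Randomization module in REDCap", so nothing in the allocation balances the arms on baseline latency.

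**The concern.** With free baseline means in each arm and complete data, a GEE containing time, group and their interaction reproduces the arm-by-time means. Its change-from-baseline contrasts are then differences in raw mean change. The fallback tests the same quantity directly. A change score subtracts the whole baseline value, whereas the best prediction of a later value from baseline has slope r when the SDs are equal. Subtracting too much has two consequences:

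- **Precision.** The variance is larger than it need be, in a trial expecting about 22 completers.
- **Sensitivity to chance imbalance.** If the arms differ at baseline, the change-score estimate moves by (1 − r) times that difference in the opposite direction. Simple randomisation of 27 people makes a noticeable difference fairly likely. The plan compares baseline characteristics between the arms but does not say what follows from an imbalance.

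At stake is some precision and protection against a chance shift in the estimate. Validity is not in question.

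**Working it through.** **Inputs.** From Accrual: difference 4.5 min, SD 4, r = 0.80, 20% attrition, 27 participants (27 × 0.8 = 21.6, taken as 22 completers, 11 per arm). From Primary outcome variable(s): measurements at baseline, 4 weeks and 16 weeks. Assumed: two-sided alpha 0.05 (not stated), equal SDs at all visits unless noted, and r = 0.5 as an illustrative lower value.

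**The plan's own figure.** For a mean of three measurements the variance factor is (1 + 2 × 0.80)/3 = 0.867. Then n per arm = 2 × (1.960 + 0.842)² × 16 × 0.867 / 4.5² = 10.75, so the total is 21.5 and 21.5/0.8 = 26.9. The stated 27 is reproduced.

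**Change score against ANCOVA, one follow-up visit.**

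- Change: variance = 2(1 − r) × SD² × 2/11
- ANCOVA: variance = (1 − r²) × SD² × 2/11 × (1 + 1/18), where 1/18 = 1/(22 − 4) is the cost of estimating the slope

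| | r = 0.80 | r = 0.5 (assumed) |
|---|---|---|
| Large-sample ratio, (1 + r)/2 | 0.90 | 0.75 |
| Net ratio, × 19/18 | 0.95 | 0.79 |
| SE, change v ANCOVA (min) | 1.079 v 1.051 | 1.706 v 1.518 |
| Power for 4.5 min (noncentral t, 20 v 19 df) | 97.7% v 98.2% | 71% v 80% |

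With 60,000 simulated trials and 22 completers, the net saving was 4.7% at r = 0.80 and 21.1% at r = 0.5.

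**Two-visit GEE with a common baseline slope, r = 0.80.** The mean of the two follow-ups, given baseline, has variance (1 + r)/2 − r² = 0.26 (in SD² units).

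- One visit: (0.36 + 0.26/18)/0.40 = 0.936
- Mean of both visits: 0.26 × (19/18)/0.30 = 0.915, where 0.30 = 1.5(1 − r) is the variance of the corresponding change

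A direct GEE simulation (2,000 runs, complete data) gave 0.933 at week 4, 0.939 at week 16 and 0.916 for the mean. With simple randomisation of 27 and 20% attrition (assumed half before each follow-up), the ratios were 0.94 and 0.97 at r = 0.80, and 0.79 and 0.80 at r = 0.5. In participants, 22/0.95 = 23.2 and 22/0.936 = 23.5, so 22 completers act like about 23 to 23.5.

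**Chance imbalance.** With 13 v 14, the baseline difference has standard error √(1/13 + 1/14) = 0.385 SD. The chance that it exceeds 0.5 SD either way is 2(1 − Φ(0.5/0.385)) = 19%, or 20% averaged over simple-randomisation splits. Such a difference (2 min or more) shifts the change-score estimate by at least 0.2 × 2 = 0.4 min at r = 0.80, or 0.5 × 2 = 1 min at r = 0.5. In the simulations the plan's GEE moved by −0.18 to −0.21 per unit of baseline difference at r = 0.80, and the covariate GEE by −0.02 to 0.01.

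**Where the gain stops.** With equal SDs, (1 + r)/2 × 19/18 = 1 gives r = 0.895. If the post-treatment SD is k times the baseline SD, ANCOVA breaks even when 0.36 × (19/18) × k² = k² + 1 − 1.6k at r = 0.80. The lower root is k = 1.06. The worst case is k = 1.25, where the slope of post on baseline is 0.8 × 1.25 = 1 and the ratio is 19/18 = 1.056.

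**The case against.** The strongest reply is that the gain is small and conditional. Both planned analyses already use baseline through change contrasts or change scores, so the comparison is with a change score and not with ignoring baseline. On the plan's own inputs the benefit is half a percentage point of power. The larger figures need r = 0.5, which the documents do not give. The gain also depends on the SDs: at r = 0.80 a post-treatment SD only about 6% above baseline removes it for one-visit ANCOVA. Equal SDs cannot be taken for granted, because the baseline week is also used for selection (latency over 30 min or wakefulness over 60 min).

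The figures also belong to a contrast that the plan does not fix as primary. The power section targets a time-averaged difference. Against an unadjusted mean of the two follow-ups, the saving at r = 0.80 would be about 70% (0.90 to 0.274 SD²) and would shrink as r falls, to about 30% at r = 0.5. Finally, participants with a baseline diary only would leave the model, while the plan promises to use all available data.

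All of this is accurate. It limits the point to a modest improvement but gives no reason to prefer the change score. For change from baseline, the worst-case loss at this sample size is about 5.6% of variance, against a saving of about 21% if r is 0.5. Baseline-only participants carry little information on change.

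**Conclusion.** The point holds as a cheap improvement, not as the correction of an error. For change from baseline at one visit, with r = 0.80, equal SDs and 22 completers, a baseline covariate saves 5% (ANCOVA) to 6% (two-visit GEE) of the variance, and about 8.5% for the mean of both follow-ups. Power on the plan's inputs is about 98% either way. The practical case is insurance: the saving grows if the correlation over 16 weeks is below the assumed 0.80, and the estimate stops moving with a chance baseline difference. These sizes apply to change from baseline, and the documents do not say whether that or the time-averaged difference is the primary test.

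**What to change.** - **Primary model.** Fit the GEE to the week-4 and week-16 values with time, group, group by time and baseline sleep latency as a covariate. State which contrast is the primary test.
- **Fallback.** Replace the change-score test with ANCOVA on baseline.
- **SF-36.** Do the same, with each score's own baseline.
- **Alternative.** A model with a common baseline mean is suitable only if the covariance is not forced to be exchangeable with one variance. With that structure, r = 0.80 and a post/baseline SD ratio of 1.25 (assumed), its variance is 1.08 times that of the change score.

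The cost is wording, one degree of freedom and a slope-estimation penalty of about 4–6% with 22 completers, already counted in the net figures. Participants with a baseline diary but no later diary no longer enter the model, so the statements on intention to treat and use of all available data need to be reworded to match. Enrolment is closed at 27, so the change should be fixed before outcomes are examined by arm.

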Study Procedures: A) Subjects: The target study population is older adults with mild cognitive impairment who have insomnia. B) Recruitment and Screening: We will recruit 27 eligible participants from three sources: 1) Division of Geriatric Medicine Division Ralston House clinic (on hold due to Covid), 2) PennSeek, and 3) Recruitment Database. After consent, subjects will be screened for key inclusion criteria. First, they must answer yes to one of the insomnia screening questions and score within the a 28-36 range on the TICS. Participants will be asked if it takes them longer than 30 minutes to fall asleep on most nights and/or if they are awake for more than 60 minutes during the nighttime period. Next, they will receive (either by mail or contactless delivery to their door) actigraph device and a tablet to complete a sleep diary for a period of one week. Once insomnia inclusion criteria are confirmed from the actigraph and diary data, we will contact participants by phone to schedule Visit 1 via videoconference. C) Randomization: All retained participants will be randomly allocated (1:1) to either intervention or control arm. D) Baseline (pre-treatment) assessments, collected at Visit 1, include sleep measures and measures of health related quality of life, physical activity, cognition, social activity, and blood samples. E) Intervention: A 4-week intervention (see intervention description below) will be provided to subjects randomized to the intervention group. Sleep diaries will be completed and actigraph device worn for all four weeks of treatment, in both groups. F) Post-intervention and Follow-up data collection (visit 2 week 5; visit 3 week 16): All baseline assessments will be repeated immediately post- intervention and at three months post-intervention follow-up (sleep measures and measures of health related quality of life, physical activity, cognition, social activity, and blood samples; one week sleep diary + actigraphy). G) Demographics: Data on demographics and other information (see measurement section) will be assessed by questionnaires at baseline, post-intervention and follow-up. Intervention: The intervention will include a meaningful activity protocol during the day and Assistive Relaxation Therapy at night. The personalized meaningful activity protocol will be developed based on the individuals factors contributing to insomnia, typical daily circadian profile, functional status, and preference for activity. The individuals typical circadian profile will be calculated from the one-week baseline accelerometer data using algorithms previously developed by [name] (co-mentor) and research team. The intervention will be broken into: 1) Sleep Hygiene Education, including content on routine, stimulus control principles, food/drink/substance intake (caffeine, alcohol, etc.), activity, naps, etc; 2) Meaningful Activity Modules a) Physical Activity, including content from the Go4Life Campaign (NIA) on endurance, strength, balance, and flexibility b) Cognitive Activity including various cognitively stimulating games and exercises such as cross-word puzzles and c) Social engagement including identifying social support persons, group activities in the area and using technology to stay connected; 3) Assistive Relaxation Therapy (ART), a breath-based relaxation application that is coupled with a physical anchoring task. After reviewing baseline assessments to determine etiological risk factors contributing to the insomnia, each participant and the PI will construct their meaningful activity plan. Thus, study participants in the intervention arm will receive (1) tablet computer with Ditti application (for ART) and REDCap application, sleep education material, and meaningful activity modules; (2) Actigraph wrist watch device. They will be instructed how to use the tablet and encouraged to use the tablet. They will be asked to complete the daily sleep diary on the tablet, use the activity modules daily as pre-determined times personalized to the participant, use ART when they get in bed and if they awake during the night to help them with their insomnia symptoms for a four-week period. They will be asked to wear the actiwatch on the non-dominant wrist to monitor sleep/wake patterns. Participants will have weekly to biweekly phone consultation with the study interventionist to receive guidance and adjustment on activity plans. Based on previous research,

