
physical, social, or cognitive activity has shown significant improvement in sleep in 2-4 weeks and ART therapy has improved sleep latency in just two weeks. Thus, we feel confident that a 4 week intervention period is sufficient and justified. As per NIH guidelines, we are providing additional details related to the intervention relevant for assessing Human Subjects Safety. The following components which will be used for the four-week intervention period. Tablet computer connected by wireless cellular phone data. Tablet-enabled sleep diary: The Sleep Diary will be administered via the REDCap, utilizing the MyCap feature. Sleep Education Information: Sleep education/sleep hygiene information will be loaded to the tablet; participants will also receive a print copy. Meaningful Activity Modules: There will be three modules related to physical, social and cognitive stimulating activity. These will be loaded to the tablet; participants will also receive a print copy. Assisted Relaxation Therapy (ART) will be loaded onto the tablet via Ditti application. We will ask the study participant to engage in an anchoring task (finger tap) on the tablet screen at the exhalation point of the breathing cycle while they are lying in bed trying to sleep. Study participants will be asked to use the ART intervention every night as they are trying to fall asleep, or when they wake up at night. They will use it every night for four weeks. For ART intervention to work, it must be used on a nightly basis when in bed. It will be administered via the tablet. These technologies do not constitute a medical device as per FDA guidance related to mobile device technologies. Actiwatch Spectrum Plus: Each participant will be given an Actiwatch Spectrum Plus (Koninklijke Philips, N.V.), a piezoelectric accelerometer worn on the non-dominant wrist. Movement data are sampled at a rate of 32 Hz, and activity counts are recorded in 60-second epochs. Additionally, the watch has Silicon photodiode light sensors, and a button that enables participants to signal when they first try to fall asleep and when they get out of bed in the morning. The button can also be used to signal naps. Periods of activity and inactivity are analyzed in order to estimate sleep/wake status. Computer programs are used to derive levels of activity/inactivity, rhythm parameters and daytime naps. Wrist actigraphy monitoring has been shown to be a reliable way to objectively monitor sleep-wake cycles. Control arm: The control arm will consist of sleep education materials. They will be asked to complete the tablet-enabled sleep diary and wear an actigraph device on the non-dominant wrist. See attached for protocol table.

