We do not believe there are any major risks associated with the proposed protocol. There is minimal risk associated with finger pricks for blood samples, physical activity, and study burden. We will explain associated risk to the participants. Other potential risks to participants are fatigue from data collection, stress in response to self-report instruments or concerns related to confidentiality. In addition, the participant may experience discomfort from sleeping with the wrist watch device, but that usually subsides after the first night. If the participant cannot tolerate the watch, he/she will be instructed that removal of the watch is allowed. Participant burden, specifically fatigue, is the most likely risk related to this study. To minimize fatigue during data collection, we chose only the most relevant self-report instruments. However, given that this is an older adult population with cognitive impairment; we will offer the participant the opportunity to take breaks. It is possible that some participants may become anxious or stressed during data collection because of the questions asked, the burden of data collection, or for other personal reasons. Stress is judged to be low likelihood because the instrument questions are not highly intrusive or sensitive. However, should this occur, the participant will be asked if they would like to terminate or delay data collection. Loss of confidentiality is considered very low likelihood given the protections we will have in place and our experience in systems of protecting private information. Intervention: The study poses minimal risks to subjects beyond standard clinical care for insomnia. Sleep hygiene is a standard clinical recommendation for insomnia, and thus does not pose any additional risks to the subject beyond standard clinical care. Furthermore, the relaxation intervention component can reduce the risk of falls or daytime sleepiness associated with the standard of care treatment, conventional CBT-I. The tablet screen background is black for the sleep diary to avoid excessive light exposure at night, and the tablet screen is set to black when using the ART intervention in bed. The tablets are locked to prevent use of other applications. Plan to address risk: Finger prick via a Lancet for blood samples might result in occasional bruising, pain, or local reaction. All blood samples will be taken by the participant using precise methods provided to them. Physical Activity: In very rare occasions, the subject may fall or get injured during physical activities. These adverse events should be minimized by using personalized physical activity plans, which will be developed/designed based on the subjects personal features by the PI to be most suitable for the subject. The activity intervention will be based on an existing NIH-funded activity protocol for older adults. Any occurrence of adverse events will be immediately reported to the IRB at the University of Pennsylvania. Wrist watch discomfort: The subject may experience discomfort from sleeping with the wrist watch device, but that usually subsides after the first night. If the subject cannot tolerate the watch, he/she will be instructed that removal of the watch is allowed. Fatigue: We estimate screening and consent to take 30 minutes, quantitative data collection 20 minutes; instructions for actigraphy and sleep diary 5-10 minutes; blood samples 5 minutes. We anticipate developing the meaningful activity plan to take 30 minutes to one hour. Stress: As the PI, I will be overseeing data collection. I am a registered nurse with a masters degree specialized in the care of older adults and a PhD. Thus, I am well trained to be supportive and helpful to the participants should they become anxious or stressed in response to survey questions. If participants do become stressed, data collection will be delayed to tend to the participants emotional needs. Data collection will resume if and when the participant is ready to proceed.

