Trial monitoring will be done by a safety monitoring committee, which includes the PI, primary mentor ([name]) a statistician ([name]) and an expert in the care of older adults ([name]). We will evaluate the progress of the study on a monthly basis, including periodic assessments of data quality (safety and integrity) and timeliness, recruitment, accrual and retention, participant risk versus benefit, and other factors that can affect study outcome; consider factors external to the study when relevant information becomes available, such as scientific or therapeutic developments that may have an impact on the safety of the participants or the ethics of the trial; review study performance; and discuss the resolution of problems. Furthermore, we will monitor adverse events (AEs), including serious adverse events (SAEs) and unanticipated problems (UPs). An Adverse Event is any untoward medical occurrence in a patient or clinical investigation participant and which does not necessarily have a causal relationship with this treatment. Participants will be queried regarding any changes in their health and medications at each contact. The informed consent document will list the daytime and after hours contact information for the site Principal Investigator. All AE and SAE reporting will be done in adherence with IRB guidelines; the PI will notify the IRB within 48 hours of any serious possible or potentially study-related AEs. The report will include the description of the AEs and any actions taken by the PI. SAEs in this population include, but are not limited to death, hospitalization, evidence of abuse, suicidal ideation, and medical emergencies. The PI will also keep a log of all AEs. Any deviations related to the protocol will be reported to the IRB using a deviation form immediately upon the discovery of the deviation. Given the non-invasive nature of the intervention, the team does not anticipate AEs beyond the average rate of these events in this population. The literature in the field will be continually appraised by the team. If any team member uncovers new information that would impact the safety of the participants or the ethics of our study, the PI and entire mentoring team will discuss the issues. At this time, given the low risk of the intervention, there is no plan for interim analyses or any stopping rules.

The following documents are currently attached to this item:

There are no documents attached for this item.

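### Falls are a named risk of the exercise module, but no fall-specific question is asked on an equal schedule in both arms, so fall counts may be incomplete and not comparable

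*Combined protocol and SAP*

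**What the plan says.** All references are to the combined protocol and SAP.

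- **The named harm.** Potential Study Risks: "In very rare occasions, the subject may fall or get injured during physical activities". The response offered is preventive: "These adverse events should be minimized by using personalized physical activity plans".
- **Who is exposed.** Procedures places the module in the intervention arm, with "content from the Go4Life Campaign (NIA) on endurance, strength, balance, and flexibility". For the other arm, "The control arm will consist of sleep education materials", plus the sleep diary and the actigraph.
- **How adverse events are found.** Data and Safety Monitoring gives one method: "Participants will be queried regarding any changes in their health and medications at each contact". The investigator keeps a log of all adverse events, and a committee reviews the study monthly.
- **How often contact occurs.** In the description of the intervention arm, Procedures says: "Participants will have weekly to biweekly phone consultation with the study interventionist to receive guidance and adjustment on activity plans". No such calls are described for controls. Both arms have Visit 2 at week 5 and Visit 3 at week 16.
- **What is recorded.** Study Instruments, and Administration of Surveys and/or Process, list no fall item. Self-reported medical conditions are collected, but a fall is not a condition. The Analysis Plan describes no adverse-event table.
- **Who reports.** Participants have mild cognitive impairment (Key inclusion criteria), and the consent overview says the intervention has no caregiver component. No informant is described.

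**The concern.** A fall that leaves no injury is not obviously a change in health, and someone with mild cognitive impairment may not volunteer it weeks later. The log, the reports to the IRB and the monthly review all depend on the fall first being mentioned.

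Tying the query to each contact creates a second problem. Contact is part of the treatment package, so the arms are asked a different number of times. A by-arm count would then mix a difference in falls with a difference in asking.

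What is at stake is the information passed on. The abstract says the pilot will inform larger trials, and the planners of those trials will want a usable fall count for the exercise component. The primary sleep-latency analysis is not affected.

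**Working it through.** **The plan's own figure.** The documents state no fall rate. The only figure used here is the sample size of 27 allocated 1:1 (Method for Assigning Subjects to Groups; Accrual), so about 13 and 14 per arm. It is not in dispute. With SD 4, difference 4.5, r = 0.80 and 80% power, and assuming three measurements and two-sided alpha 0.05, n per arm = 2 × (1.960 + 0.842)² × 16 × (2.6/3) / 20.25 = 10.75. Then 2 × 10.75 / 0.8 = 26.9, so 27.

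**1. Opportunities to report a fall after baseline**

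| Period | Intervention | Control |
|---|---|---|
| Calls in 4 weeks, biweekly to weekly | 4/2 = 2 to 4/1 = 4 | none described |
| Visit 2 (week 5) | 1 | 1 |
| Between Visits 2 and 3 (16 − 5 = 11 weeks) | none described | none described |
| Visit 3 (week 16) | 1 | 1 |
| Total | 4 to 6 | 2 |

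The Analysis Plan mentions calls to remind participants about the diary. These could reach either arm, but they depend on missed entries and are not a schedule. About 11 of the 15 post-baseline weeks (4 + 11), or 73%, fall in the stretch with no described contact.

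**2. Effect of unequal capture.** Recorded rate ratio = true ratio × (capture in intervention / capture in control). The capture values are assumptions; the documents give none.

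| Capture, intervention / control | True ratio 1 | True ratio 2 |
|---|---|---|
| 0.90 / 0.50 | 1.80 | 3.60 |
| 0.75 / 0.50 | 1.50 | 3.00 |
| 0.75 / 0.75 | 1.00 | 2.00 |
| 0.50 / 0.90 | 0.56 | 1.11 |

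The call schedule points to the first two rows, an inflated intervention excess. The last row cannot be excluded: a participant might treat a stumble during exercise as part of the activity and not mention it.

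**3. Effect of incomplete capture on the count in the exercising arm.** Assume 0.3 to 1.2 falls per person-year (not in the documents). Expected falls = 13 × weeks/52 × rate, and P(none recorded) = exp(−expected × capture).

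| Window | Person-years | Expected falls | P(none), full capture | P(none), half capture |
|---|---|---|---|---|
| 4 weeks | 1 | 0.3 to 1.2 | 74% to 30% | 86% to 55% |
| 16 weeks | 4 | 1.2 to 4.8 | 30% to 1% | 55% to 9% |

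**4. What the trial could show with perfect capture.** With no falls among 13 participants, the exact one-sided 95% upper bound on fall risk is 1 − 0.05^(1/13) = 20.6%. With no fallers among 14 controls, Fisher's exact test gives p = 0.098 for 3 of 13 intervention fallers and p = 0.041 for 4 of 13. These limits come from the sample size, not from the wording of the question.

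**The case against.** The strongest reply is that the exercising arm is the better watched one. During the four weeks of exercise it is asked about health every one to two weeks, in calls about the activity plan itself. Impairment is mild by eligibility, and participants must answer four of five consent questions correctly. The risk section already treats a fall during activity as an adverse event, so a reported fall would be logged. The committee includes an expert in the care of older adults. The plan calls falls very rare, and a general query is a common choice in a small minimal-risk pilot. The protocol table is said to be attached but is not in the text, so a fall item there cannot be ruled out.

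Much of this stands. A reader might infer that the plan will miss a fall signal in the intervention arm. The documents do not support that as the likely failure: the calls shorten recall in that arm during exercise, and if anything favour an inflated excess.

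The reply does not make the arms comparable, supply a definition of a fall, or cover weeks 5 to 16. The log records only what is reported.

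**Conclusion.** The point holds as one of incomplete and unequal ascertainment. Falls are a named risk, nothing in the available text asks about them directly, and the general query is tied to contacts that number about 4 to 6 in one arm and 2 in the other. Under the assumed capture values, equal true rates could be recorded as a ratio anywhere from 0.56 to 1.8. The direction cannot be settled from the documents.

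Three further inferences should be resisted:

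- The statement that "the team does not anticipate AEs beyond the average rate of these events in this population" is an expectation. It is not a criterion or a test against which the trial judges safety.
- The absence of falls from the examples of serious events is no defect. That list is expressly open, and a fall without injury would not ordinarily be serious.
- The 20.6% bound is not a consequence of the query. Better wording would not change it.

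The conclusion assumes that the unseen attachments hold no fall item and that controls receive no regular calls. It is a modest point that is cheap to correct and bears on what the pilot can report about safety.

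**What to change.** In Data and Safety Monitoring, add one defined fall question: number of falls since the last assessment, whether injured, and whether during a study activity. Ask it in the same words in both arms at the already scheduled Visits 2 and 3, and at Visit 1 as history where that is still possible.

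Log each fall as an adverse event with its source: the fixed question, or volunteered at a call. Add to the Analysis Plan a by-arm table based on the fixed-visit answers only, showing the number asked per arm. Falls volunteered at calls stay in the log but out of the comparison, because controls have no matching calls.

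**Cost.** One short REDCap item and an amendment, with no new visit and no change to the sample size.

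**Downsides.** Recall runs over about 4 and 11 weeks in people with mild cognitive impairment, so equal asking is gained at the price of a longer interval than the calls give. The modification form reports enrollment closed at 27, so those who have finished will have no answers and Visit 1 may be past for many. The table should be labelled descriptive.
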